7.4 Power Analyses

A recent study indicated a medium effect size (Cohen's $d = 0.46$) for CBD treatment that increased plasma AEA levels compared to an antipsychotic drug control condition²⁶. Preclinical models of neuropathic pain in mice demonstrate that FAAH inhibitors decrease hyperalgesia

and allodynia with large effect sizes (Cohen's $d = 4-5$)¹⁸. Our pilot HRV data indicate a medium to large effect size (Cohen's $d = 0.8$) for reduced RMSSD in PLWH with neuropathic pain compared to PLWH without neuropathy. We conducted power calculations with the G*POWER software⁹² comparing the area under the curve (AUC) of the change from baseline in pain levels between the three doses of cannabis. The actual analyses will have higher power, since they rely on a longitudinal mixed-effects model. With $n=100$ participants completing the cross-sectional baseline visits, and measured in a within-participant design, as described above, we have 80% power to detect an effect size Cohen's $f=0.180$. This Cohen's f corresponds to a range of group means for the three groups corresponding to a small-to-medium Cohen's $d = 0.382-0.441$. We have 0.61-0.76 power to detect such a pairwise difference as statistically significant in post-hoc analyses (e.g., with Bonferroni correction for post-hoc comparisons). If the completion rate at this stage is 95% (90%) of the initial enrollment of $n=100$, the detectable effect size is Cohen's $f=0.185$ (0.190). These correspond to a range of group means for the three groups corresponding to small-medium Cohen's $d = 0.403-0.465$.

For Aim 2, with 20% attrition over the 6 months of IMPACT we have $n= 80$ participants with 6 months (26 weeks) of data. We conservatively ignore the drop-out participants (who nonetheless contribute partial data). Assume, conservatively, that participants will use cannabis on average 2 times/week. This gives $n=80$ and $k=52$ observations/participant. If ICC is the intra-class, or within-participant correlation, the effective sample size (number of equivalent independent observations) is $n_{\text{eff}} = n/(ICC+(1-ICC)/k) \approx n/ICC$ [e.g., Killip, Mahfoud, Pearce, Ann Fam Med, 2004; 2:204-208.]. Assuming conservatively $\rho=0.5$ (or lower), we get $n_{\text{eff}} = 2n = 200$ [$n_{\text{eff}} = 160$]. We have 80% power to detect a (partial) correlation R between the individual predictors (Hypothesis 1: CBD, THC, and the CBD/THC ratio; Hypothesis 2: pain levels and HRV) and change in pain of $R = 0.218$ (or semi-partial $R^2 = 0.0475$), after adjusting for confounders. Calculations used G*Power.

For Aim 3, assuming $n = 80$ participants complete the 6-month follow-up, we have 80% power to detect an association between an individual predictor and response (e.g., total CBD and changes in neuropathic pain levels) of $R = 0.302$ (or semi-partial $R^2 = 0.092$), after adjusting for confounders. The calculations used G*Power.

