4.2 Cannabis Administration Protocol

Participants will receive vaporized cannabis using Volcano vaporizers (Storz and Bickel) with the aforementioned concentrations of CBD and THC at each of three visits. Allocation assignment of visits will be assigned using randomization schedule prepared by our statistician. The allocation schedule will be kept in the pharmacy and concealed from other study personnel. The cannabis will be stored in a freezer at 20°C until the day before use. At least 12 hours before each session, 800 mg of study cannabis will be thawed. The vaporization session will be performed in a HNRP negative pressure room designed to prevent the vapor from being transferred to rooms in which other occupants of the building are working. Puffs from the vaporizer balloon will be standardized so that a consistent amount is inhaled. This will be done according to a cued-smoking procedure shown to produce reliable increases in plasma THC levels⁶⁵. A nurse will provide instructions to participants to 'inhale' (5 seconds), 'hold smoke in lungs' (10 seconds), and 'exhale' and to wait before repeating the puff cycle (40 seconds). Each participant will inhale 4 puffs at each session, an amount that was well tolerated during our previous human laboratory experiments⁶⁰. We will measure vital signs (heart rate, respiration), pain intensity measured by a 0 to 10 numerical rating scale, and HRV at baseline (30 minutes before cannabis administration), at time zero (immediately after cannabis administration), and at 60, 120, and 180 minutes after drug administration. As a secondary measure of pain relief, we will use the Patient Global Impression of Change (PGIC) that will be measured hourly following administration of study medications. We will also conduct a von Frey assessment. The von Frey tool consists of monofilaments that are applied to the skin until bending of the filament occurs, calibrated to a specific pressure and designed to minimize movement artifacts⁶⁶. Increased pain to von Frey stimulation occurs in NP and clinical trials indicate that cannabis treatment can reduce allodynia on this test⁶⁷. We will include this measure in our battery and assess pain using the VAS as previously reported⁶⁷; the von Frey filament will be applied on the dorsum of the more painful foot until bending is observed for 3 seconds, followed by a VAS pain rating.

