7.0 STATISTICAL ANALYSIS PLAN

7.1 Aim 1 Measures and Analyses

Data will be assessed for normality and transformations applied as needed (e.g., log). Neuropathic pain before and after acute cannabis administration will be assessed by NPRS and the von Frey test. Plasma AEA and 2-AG will be measured with LC/MS. Flow cytometry will quantify the percentage of PBMC that express CB2, FAAH, and MAGL, including monocytes, CD4+ T-cells, and CD8+ T-cells. To examine the effect of different CBD/THC products on NP and EC biomarkers, we will use a linear mixed model with subjects treated as a random effect to model the response measures. This methodology takes into account the repeated measures aspect of the within-subjects crossover study design, incorporating information from observations for each subject at different treatment doses and multiple time points within each dose. For initial modeling, terms will include dose (0.01%, 5.1% - 4 puffs, and 5.1% - 8 puffs) CBD treated as a categorical variable), time (0, 60, 120 and 180 minutes after exposure treated as a continuous variable), and dose x time interaction. Additional terms will also be included for the sequence in which the treatments were administered (e.g., low CBD vs. medium CBD) and for second-order time (time²). The quadratic term is intended to model a U-shaped response curve if responses initially increase (or decrease), reach a maximum (or minimum), then decrease (or increase) back to baseline levels. For each outcome measure, each of these last 2 terms will be omitted from subsequent models and not reported if nonsignificant. Any potential factors that associate with outcome variables at the $\alpha = 0.20$ level in single-predictor analyses (history of light vs. heavy cannabis use, mode of prior cannabis use – i.e., engaging in smoking, or vaporizing, or both), time since last cannabis use before baseline, duration of cannabis use over lifetime, presence of adolescent cannabis use, duration of HIV infection, nadir CD4, viral load, gender, the presence of other non-cannabis analgesic medications, history of non-cannabis substance use disorders) will be included in the linear model. Dose effects at each time point will be assessed with mixed modeling after re-coding time as a categorical factor and including dose and dose x time terms (plus a term for sequence if this is significant in the initial model). Differences among doses will be evaluated using the Tukey honestly significant difference (HSD) comparison tests for differences of effects over all time points and contrasts within each

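### The claim in Section 7.4 that the mixed model has more power than the AUC-of-change calculation is unsupported: the Aim 1 model does not say how session pre-dose pain enters and has no session-level random effect

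*Combined protocol and SAP*

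**What the plan says.** Section 7.4 bases the Aim 1 power on "comparing the area under the curve (AUC) of the change from baseline in pain levels between the three doses of cannabis", with 100 "participants completing the cross-sectional baseline visits, and measured in a within-participant design". It reports 80% power at Cohen's f = 0.180 and then adds, without condition, "The actual analyses will have higher power, since they rely on a longitudinal mixed-effects model". For pairwise comparisons it says "We have 0.61-0.76 power to detect such a pairwise difference as statistically significant in post-hoc analyses".

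Section 7.1 describes the model. Subject is the random effect. The terms are dose, "time (0, 60, 120 and 180 minutes after exposure treated as a continuous variable", dose by time, sequence, time squared, and covariates screened at the 0.20 level. Pre-dose pain is neither a time point nor a listed covariate, and the response is not said to be a change from baseline. The later sentence in Section 7.1 on random intercepts and slopes follows the pain–HRV association model and names no session effect.

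Section 4.2 has pain rated "at baseline (30 minutes before cannabis administration" at each session, so the value exists. Section 7.2 adjusts the Aim 2 model for baseline pain as an addition to the Aim 1 covariates, which confirms that it is not on the Aim 1 list.

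**The concern.** The calculation in Section 7.4 uses the session baseline; the model in Section 7.1, as written, does not mention it. With complete data and a valid session-level error term, a mixed model tests the overall dose effect on session means, so having four ratings per session gives nothing that the AUC summary lacks. What can differ is the treatment of the baseline. If it is left out, day-to-day variation in a participant's pain stays in the error, and power may go up or down.

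Two things are at stake. The sentence offers reassurance in a section where pairwise power is already only 0.61 to 0.76. And a dose model with no session-level random effect treats the four ratings of one session as more independent than they are likely to be, which affects the type I error rate.

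**Working it through.** **1. The plan's own figure.** Repeated-measures F test, three doses, two-sided 5% level (Section 7.1), n = 100. Noncentrality λ = f² × 3n / (1 − ρ), where ρ is the correlation of the AUC-of-change scores between doses; df = 2 and 2(n − 1) = 198.

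- ρ = 0: λ = 0.180² × 300 = 9.72, critical value 3.04, power 0.797. The plan's figure reproduces.
- n = 95, f = 0.185: power 0.799. n = 90, f = 0.190: power 0.798. Both reproduce.
- ρ = 0.5: λ = 19.44, power 0.98. This does not reproduce, so the plan's figure takes no credit for correlation between doses.
- The d range also reproduces: 0.180 × 6/√8 = 0.382 and 0.180 × √6 = 0.441.

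**2. Variance model (assumed; the documents give no components).** Rating = participant + session within participant (variance s) + measurement error (variance 1). The AUC is taken as the mean of four post-dose ratings; trapezoid weights move the powers by about 0.01. For doses compared within participant, the variance of the session summary is:

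- change from baseline: 1 + 1/4 = 1.25
- post-dose mean, baseline not used: s + 0.25
- post-dose mean, baseline as covariate with within-participant slope s/(s + 1): s + 0.25 − s²/(s + 1) = 0.25 + s/(s + 1)

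The third is below both of the others for every s > 0.

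**3. Power at the effect that gives the change analysis its stated 80%.** λ = 9.72 × 1.25 / variance, ρ = 0, session-level error with 198 df.

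| s | Post-dose only: variance, λ, power | Baseline-adjusted: variance, λ, power |
|---|---|---|
| 0.5 | 0.75, 16.20, 0.96 | 0.583, 20.83, 0.99 |
| 1 | 1.25, 9.72, 0.80 | 0.75, 16.20, 0.96 |
| 2 | 2.25, 5.40, 0.53 | 0.917, 13.25, 0.91 |

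**4. Sensitivity to ρ.** If change scores do correlate across doses, λ is divided by (1 − ρ). Post-dose-only power at s = 2 becomes 0.66 at ρ = 0.25 and 0.84 at ρ = 0.5. It falls below the plan's 80% once s exceeds 1.25/(1 − ρ) − 0.25, which is 1.00, 1.42 and 2.25 at ρ = 0, 0.25 and 0.5.

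**5. Subject random effect only, raw post-dose scores.** With 100 × 3 × 4 = 1,200 ratings, the residual has 1,200 − 100 − 11 = 1,089 df, of which 198 are at session level. The dose mean square has null expectation 1 + 4s; the residual mean square has expectation 1 + 4s × 198/1,089 = 1 + 0.727s. The ratios are 2.20, 2.89 and 3.67 at s = 0.5, 1 and 2. The chance of exceeding the 5% critical value (3.00) is about exp(−3.00/ratio) = 0.26, 0.35 and 0.44. Simulation gives similar rates, up to 0.27, 0.35 and 0.46.

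**The case against.** A reader might infer that the plan discards the baseline and that its power is therefore below 80%. The documents do not support that. Section 7.1 leaves the response undefined, and nearby text treats pain relative to the pre-dose level: it speaks of pain before and after administration, of a curve that returns to baseline, and of a 30% reduction. Section 7.2 uses laboratory change scores. If change is the response, the omission of the baseline from the time axis is expected. This stands, and so the defect is an unspecified response, not a demonstrated loss. But under that reading, with complete data and a valid error term, the variance is 1.25 for both analyses: a tie, not a gain. The four changes in a session would also share the error of one baseline rating, so a session-level term is still needed.

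The mixed model does have real advantages. Section 7.1 keeps participants who miss sessions and allows covariates. The first is modest on the plan's own figures: going from full to 90% completion moves the detectable f only from 0.180 to 0.190. The gain from covariates is not quantified.

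The powers in the table also do not belong to the model as literally written, which lacks the session effect. That model rejects more often, but with the false-positive rates in step 5 its rejection rate is not usable power.

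Finally, the disputed sentence does not feed into the calculation. The sample size and f = 0.180 stand without it.

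**Conclusion.** The statement of higher power is not supported by the analysis that Section 7.1 describes. Whether power is above or below the AUC-of-change figure depends on how pre-dose pain enters and on a variance ratio that the documents do not give. For raw post-dose scores with a valid session-level error term, it ranges from about 0.96 to 0.53 as session variance goes from half to twice measurement variance, at the ρ = 0 that reproduces the plan; the crossing moves higher if change scores correlate across doses.

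Baseline adjustment is the better choice in every case computed, at 0.91 or more. This assumes no carryover into the pre-dose rating; Section 2.0 specifies three separate days but states no minimum interval.

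The missing session effect is the more serious risk if session effects are real and raw scores are modelled with subject as the only random effect: the dose test then runs well above 5%. None of this shows that the trial is too small.

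**What to change.** In Section 7.1, define the Aim 1 pain response, add each session's pre-dose NPRS as a covariate (and the matching pre-dose value for other outcomes measured before each dose), and add a participant-by-session random effect. Entering the pre-dose value as participant mean plus session deviation keeps the slope within participant, as the figures above assume.

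In Section 7.4, delete the sentence on higher power, or replace it with a power figure for that model under stated session variance, measurement variance and between-dose correlation.

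The cost is SAP wording and one recalculation. Section 4.2 already collects the pre-dose pain ratings.

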8.0 PARTICIPANTS

8.1 Monitoring

The study team will review all adverse events during the study by cumulative reports on a monthly basis. A Data Monitoring Committee (DMC) will review the study for safety yearly. The study will only be stopped early if there are serious safety concerns.

The following items will be included in the yearly DMC meetings:

- Progress of the study, including participant recruitment, accrual and retention.
- Number of premature discontinuations and reasons for discontinuation

- Compliance with study treatment and adherence to IMPACT
- Safety and treatment toxicity, including summary of any AE and SAE
- Any protocol violations

8.2 Institutional Review Board (IRB) Review and Informed Consent

This protocol and the informed consent document and any subsequent modifications will be reviewed and approved by the IRB responsible for oversight of the study. A signed consent form will be obtained from the participant (or parent, legal guardian, or person with power of attorney for participants who cannot consent for themselves). The consent form will describe the purpose of the study, the procedures to be followed, and the risks and benefits of participation. A copy of the consent form will be given to the participant, parent, or legal guardian, and this fact will be documented in the participant's record.

8.3 Participant Confidentiality

All laboratory specimens, evaluation forms, reports, and other records that leave the site will be identified by coded number only to maintain participant confidentiality. All records will be kept locked. All computer entry and networking programs will be done with coded numbers only. Clinical information will not be released without written permission of the participant, except as necessary for monitoring by the, IRB and/or DMC.

8.4 Study Discontinuation

The study may be discontinued at any time by the IRB and/or DMC as part of their duties to ensure that research participants are protected.

